after the last dose of the last study drug (except for subjects who died, withdrew consent and objected to further data collection or were lost to follow up).

There will be no formal assessment of the overall survival in this study.

Arm 1 - Part 1 (Safety Run-in of Mirdametinib in Combination with Fulvestrant)

If permitted by the acceptable safety profile of mirdametinib 4 mg BID in combination with the standard recommended dose of fulvestrant, the Part 1 in Arm 1 of the study will be conducted as a single dose level. Patients with any MAPK pathway activating alteration as listed in section 6.1 will be included in this safety run-in, however patients harboring NF1 loss of function mutations will be prioritized, at the discretion of the principal investigator.

If mirdametinib 4 mg BID in combination with the standard recommended dose of fulvestrant is not tolerated well in the initial Dose Level, then a Dose Level de-escalation will be evaluated with mirdametinib 2 mg BID in combination with the standard recommended dose of fulvestrant. The Dose Level de-escalation will be evaluated according to the 3+3 design based on the incidence of dose-limiting toxicities (DLT) and the overall safety profile of the study treatments. The DLT definitions are listed in [Section 15.3](#).

At each step of the 3+3 design, the investigators will review all available safety and PK data at the current dose level and decide about the appropriate next step. The subjects will become evaluable for the 3+3 decisions if they complete Cycle 1 and receive at least 80% of doses at their assigned mirdametinib doses and all of their fulvestrant doses, or if they exhibit a DLT in Cycle 1.

Dose Selection: We note that the dosing of mirdametinib in the most recent phase II trial⁶ is 2 mg/m² twice daily, which translates to 4 mg twice daily in an adult population. However, the aforementioned study used an intermittent 3 weeks on / 1 week off schedule. This protocol is slightly different in that we are initiating a continuous dosing schedule of mirdametinib rather than intermittent. We believe that this schedule remains quite safe given that this dose is far below the MTD (15 mg BID) at which intermittent dosing was necessary to avoid toxicity.

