At each step of the 3+3 design, the investigators will review all available safety and PK data in the current Dose Level and decide about the appropriate next step. The subjects will become evaluable for the 3+3 decisions if they complete Cycle 1 and receive at least 80% of assigned drug doses, or if they exhibit a DLT in Cycle 1.

The starting dose of mirdametinib as single agent in each Dose Level escalation will be as follows:

- Dose Level 1: **mirdametinib 4 mg BID PO**, given continuously
- Dose Level 2: **mirdametinib 6 mg BID PO**, given continuously
- Dose Level 3: **mirdametinib 8 mg BID PO**, given continuously
- The de-escalation (Dose Level -1) may evaluate **mirdametinib 3 mg BID** given continuously, and (Dose Level -1INT) may evaluate **mirdametinib 3 mg BID** given on a 3 weeks on, 1 week off schedule. These de-escalation Dose Levels will be evaluated at investigator's discretion after the higher dose of mirdametinib is not tolerated. The de-escalation Dose Levels will be started only if the benefit-risk ratio is acceptable at the investigator's opinion.

The 3+3 decisions in Part 1 of Arm 2 will be made as follows.

1. Dose Level 1 (**mirdametinib 4 mg BID PO** given continuously)
 - a. Up to 3 subjects will be treated with mirdametinib as single agent at the dose of **4 mg BID PO** given continuously.

Memorial Sloan Kettering Cancer Center
[name]
[name]

- b. If 1 of the first 3 evaluable subjects in Dose Level 1 exhibit a DLT in Cycle 1, then Dose Level 1 will be expanded (see #2 below)
- c. If 0 of the first 3 evaluable subjects in Dose Level 1 exhibit a DLT in Cycle 1, then the dose of mirdametinib as single agent will be escalated to Dose Level 2 (**6 mg BID** given continuously) (see #4 below)

2. Dose Level 1 expansion:

- a. A sufficient number of subjects will be treated with mirdametinib as single agent at the dose of **4 mg BID PO** given continuously to accrue 6 evaluable subjects.
- b. If ≤ 1 of 6 evaluable subjects in the starting Dose Level exhibit a DLT in Cycle 1, then the dose of mirdametinib as single agent will be escalated to Dose Level 2 (**6 mg BID** given continuously) (see #5 below).
- c. If ≥ 2 of the first 3 evaluable subjects or ≥ 2 of the 6 evaluable subjects in Dose Level 1 exhibit a DLT in Cycle 1, then the mirdametinib dose will be de-escalated (see #3 below).

3. Dose Level -1 (de-escalation Dose Level **3 mg BID PO** given continuously)

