10.1 Mirdametinib Study Treatment

- Subjects will be instructed to take mirdametinib at home and record the time of intake for both daily doses in the patient dosing diary. Missed doses will also be recorded in the dosing diary. Subjects will be instructed to **not** take their planned morning dose of mirdametinib prior to each study visit during the treatment period. Instead, the morning dose will be taken following the pre-dose PK blood draw or any other assessment scheduled to be obtained at pre-dose during the visit.
- Mirdametinib treatment will be dispensed to subjects every two Cycles during scheduled study visits as described in the SoA or at an unscheduled visit if mirdametinib treatment is damaged/lost.
- Throughout the treatment period, subjects will self-administer study treatment BID utilizing a continuous dosing schedule in 28-day Cycles.
- Subjects will be instructed to swallow capsules whole and not to open or chew them prior to swallowing.
- No capsule should be ingested if it is broken, cracked, or otherwise not intact.
- Subjects should be encouraged to take their dose approximately every 12 hours
- Subjects can take mirdametinib capsules without regard to food intake.
- Delivery of mirdametinib via nasogastric tube or gastrostomy tube is not allowed.
- If a subject misses a scheduled dose of study treatment, and it is within 6 hours of the scheduled dose, the subject should immediately administer the missed dose and resume study treatment in accordance with the normal administration schedule. If more than 6 hours has elapsed since the time of scheduled administration, the subject will **not** be instructed to administer the missed dose and to resume study treatment as prescribed.
- Subjects should not take 2 doses together to “make-up” for a missed dose.
- If a subject vomits any time after taking a dose, then they must be instructed not to take another dose to “make up” for vomiting, but rather, to resume subsequent doses as prescribed.

Memorial Sloan Kettering Cancer Center
[name]
[name]

- If a subject inadvertently takes 1 extra dose, then the subject should not take the next scheduled dose of study treatment. Only one dose should be skipped in this context.

The dose levels for mirdametinib are summarized as follows:

Dose Level -2INT	2mg PO BID, 3 weeks on/1 week off
Dose Level -2	2mg PO BID given continuously
Dose Level -1INT	3mg PO BID, 3 weeks on/1 week off

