13.3 Evaluable subjects

Patients who achieve sufficient compliance with the study drug intake in Cycle 1 (received at least 45 of 56 [greater than 80%] doses of mirdametinib (in Arm 1 only, also both doses of fulvestrant) **or** experience a DLT will be considered as evaluable for the assessment of the DLT rate for the particular dose level.

Additional patients should be enrolled at the same dose level as necessary to ensure an adequate number of DLT-evaluable patients.

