14.0 BIOSTATISTICS

14.1 Analysis Populations

The following analysis populations will be used:

- **DLT Evaluable Population** consists of patients who receive at least 80% of planned total doses of mirdametinib in cycle 1 (in Arm 1 only, also both doses of fulvestrant) and are observed within 28 days following the first dose of mirdametinib or patients who experience a DLT.
- **Efficacy Population**, used for the assessment of efficacy for each arm, will consist of all patients in Part 2 who received at least 1 dose of study drug and who have at least 1 post-baseline tumor assessment. Arms 1 and 2 will be analyzed separately. In addition, patients treated at the MTD in the dose escalation portion of the protocol (both arms 1 and 2) will be included in the efficacy analyses for the expansion cohorts in part 2 if they meet the requirements for efficacy population as defined above. Additionally, the RP2D will be determined pending the clinical data obtained in the dose escalation portion of the protocol. If the RP2D is less than the MTD, then patients treated at the RP2D in the dose escalation portion of the protocol (both arms 1 and 2) will be included in the

Memorial Sloan Kettering Cancer Center
[name]
[name]

efficacy analyses for the expansion cohorts in part 2 if they meet the requirements for efficacy population as defined above.

- **Pharmacokinetic Population**, used for the assessment of pharmacokinetic endpoints, will consist of all patients who have sufficient pharmacokinetic concentration data recorded to derive pharmacokinetic endpoints.
- **All treated population or safety population:** consisting of all patients who receive any amount of drug

Arms 1 and 2 will be analyzed separately throughout the study.

Arm 1

The study will follow a standard 3+3 dose escalation schema. As described previously in section 4.2, the 3+3 decisions in Part 1 of Arm 1 will be made starting with a mirdametinib starting dose level (4 mg BID PO), where subjects will be treated with mirdametinib 4 mg BID PO given continuously in combination with the recommended dose of fulvestrant. If ≤ 1 of the first 3 DLT evaluable subjects in Dose Level 1 exhibit a DLT in Cycle 1, then Dose Level 1 will be expanded. Mirdametinib dose in combination with fulvestrant will not be escalated above the 4 mg BID given continuously dose level.

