15.3 Dose Limiting Toxicities

The severity of adverse events (AEs) reviewed as potential dose-limiting toxicity (DLT) will be graded according to the CTCAE V.5.0. classification.

The occurrence of any of the following AEs during Cycle 1 (Day 1 – Day 28) will be considered a DLT, except for those AEs clearly related to disease progression or intercurrent illness.

Hematologic:

1. Grade 4 or greater hematologic toxicity (neutropenia, thrombocytopenia, or anemia)
2. Grade 3 febrile neutropenia (absolute neutrophil count [ANC] < 1000/mm³ with a single temperature of > 38.3°C (101°F) or a sustained temperature of ≥ 38°C (100.4°F) for > 1 hour)
3. Grade 3 thrombocytopenia with clinically significant bleeding

Non-hematologic:

1. Grade 2 or greater ocular toxicities leading to reduced visual acuity limiting ADL, glaucoma, retinal detachment, or retinal vascular disorder
2. NYHA class III or IV left ventricular dysfunction
3. Grade 3 or greater non-hematologic toxicity that is clinically significant with the following exceptions:
 - a. Toxicity (other than rash) that starts to resolve within 3 days of initiating optimal supportive care
 - b. Grade 3 rash that resolves to grade 1 or less within 7 days of initiating optimal supportive care
 - c. Grade 3 laboratory abnormalities that are not associated with clinical sequelae (e.g., isolated lactate dehydrogenase elevation) and resolves to Grade ≤1 within 3 days of initiating optimal supportive care
 - d. Grade 3 or 4 electrolyte laboratory abnormalities that last up to 72 hours, are not clinically complicated, and resolve spontaneously or respond to conventional medical interventions
 - e. Grade 3 or 4 amylase or lipase elevation that is not associated with symptoms or clinical manifestations of pancreatitis
 - f. Alopecia
4. Grade 4 non-hematologic toxicity, with the exception of those listed above, regardless of clinical significance or duration
5. Hy's law criteria (Grade ≥ 2 bilirubin in conjunction with grade ≥2 transaminase and without elevation of alkaline phosphatase)

In addition, clinically important or persistent toxicities not included above may also be considered a DLT at the discretion of the investigator after consultation with the SpringWorks physician.

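### Section 13.3 sets DLT evaluability at a fixed 45 of 56 doses, which cannot be reached on the intermittent levels and drops the assigned-dose condition that section 4.2 applies in Arm 1

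*Combined protocol and SAP*

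**What the plan says.** Evaluability for DLT is stated in four ways. In all of them a patient with a DLT is evaluable.

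- **Section 4.2, Arm 1 Part 1.** Patients without a DLT must complete Cycle 1 and "receive at least 80% of doses at their assigned mirdametinib doses and all of their fulvestrant doses".
- **Section 4.2, Arm 2 Part 1** (repeated in 14.1). They must "complete Cycle 1 and receive at least 80% of assigned drug doses".
- **Section 13.3, both arms.** Patients who "received at least 45 of 56 [greater than 80%] doses of mirdametinib" (and, in Arm 1, both fulvestrant doses) are "evaluable for the assessment of the DLT rate for the particular dose level".
- **Section 14.1, DLT Evaluable Population.** This consists of "patients who receive at least 80% of planned total doses of mirdametinib in cycle 1", with both fulvestrant doses in Arm 1 and observation over 28 days.

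The table in section 10.1 includes two intermittent levels. Dose Level -2INT is "2mg PO BID, 3 weeks on/1 week off", and Dose Level -1INT is 3 mg BID on the same schedule.

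Some patients can be cut to a lower dose in Cycle 1 without having a DLT. Section 15.3 exempts, among others, "Grade 3 rash that resolves to grade 1 or less within 7 days of initiating optimal supportive care", while Table 4 in section 15.4 requires a restart at the next lower dose after Grade 3 or worse rash. Table 5 takes 4 mg BID to 2 mg BID. Section 15.4 does not allow re-escalation.

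**The concern.** Six evaluable patients decide the RP2D at a dose level, so the plan should leave no doubt about who they are. Section 13.3 creates two difficulties.

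First, its fixed count suits a continuous 28-day schedule only. On the two intermittent levels the threshold exceeds the number of doses planned. These are the last levels before an arm is discontinued, so an unworkable denominator there would matter.

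Second, 13.3 counts doses regardless of strength. A patient who spent most of Cycle 1 on 2 mg BID could be entered as DLT-free evidence for 4 mg BID. Under the Arm 1 rule in 4.2 the same patient would be replaced. Any resulting error favours the higher dose.

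**Working it through.** **The plan's own figure.** A cycle has 28 days (4.2) and dosing is twice daily (10.0), so 28 × 2 = 56 doses. 0.80 × 56 = 44.8, which rounds up to 45; 45/56 = 80.4% and 44/56 = 78.6%. The 45 of 56 in 13.3 is right for a continuous schedule.

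**Intermittent levels.** Three weeks on gives 21 × 2 = 42 doses. Since 42 < 45 (42/56 = 75%), full compliance still fails 13.3. An 80% rule applied to the planned doses gives 0.80 × 42 = 33.6, so 34 of 42 (81.0%). Under a literal 13.3 only patients with a DLT are evaluable on -2INT and -1INT, and the requirement of at most 1 DLT in 6 could not be met.

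**Continuous 4 mg level.** Let a be the doses taken at 4 mg, b those taken at 2 mg and m those missed, with a + b + m = 56. Take a patient with no DLT, Cycle 1 completed and both fulvestrant doses given.

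- 4.2 Arm 1 requires a ≥ 45.
- 13.3 requires a + b ≥ 45, that is m ≤ 11.
- The rules disagree when a ≤ 44 and m ≤ 11. Enumerating every split of 56 doses gives 540 that pass 13.3 and fail 4.2, and none the other way.

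Example: Days 1–7 at 4 mg (14 doses), a hold on Days 8–12 for an exempt Grade 3 rash (10 missed), then Days 13–28 at 2 mg (32 doses). Doses taken are 46/56 = 82.1%, so the patient is evaluable under 13.3. Doses at 4 mg are 14/56 = 25%, so the patient is not evaluable under 4.2. Under 14.1 the answer depends on what is counted: 82.1% by administrations, but (14 × 4 + 32 × 2)/(56 × 4) = 120/224 = 53.6% by milligrams. A hold of 6 days or more misses at least 12 doses and fails both rules.

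**Effect on the RP2D.** Let d be the DLT rate and q the share of treated patients inside this window. The documents give neither value, so both are assumptions. 4 mg BID is declared if at most 1 of 6 evaluable patients has a DLT. Counting window patients gives P(Bin(6, d) ≤ 1). Replacing them gives the same formula with d/(1 − q).

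| d | q | Counted (13.3) | Replaced (4.2) |
|---|---|---|---|
| 20% | 2% | 65.5% | 64.5% |
| 20% | 5% | 65.5% | 63.0% |
| 20% | 10% | 65.5% | 60.1% |
| 30% | 2% | 42.0% | 40.7% |
| 30% | 5% | 42.0% | 38.7% |
| 30% | 10% | 42.0% | 35.1% |

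The direction is fixed. The six patients counted under 4.2 include every DLT among the six counted under 13.3, plus any DLT in the replacements. The difference between the columns is therefore also the chance of opposite decisions. At d = 20% that is about 2.6 points for q = 5% and 5.4 for q = 10%; a simulation of 200,000 run-ins gave 2.6% and 5.4%.

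**Chance of opening -2INT.** It opens only after 4 mg and 2 mg continuous both fail. Assuming six evaluable patients at each level, the probability is the product of P(Bin(6, p) ≥ 2) at the two doses. For assumed DLT rates at 4 mg/2 mg of 20%/10%, 20%/20% and 30%/20% this is 0.345 × 0.114 = 4%, 0.345 × 0.345 = 12% and 0.580 × 0.345 = 20%.

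**The case against.** The strongest reply is that 13.3 does not govern the 3+3 decisions. Section 4.2 defines who is evaluable for those decisions, and 14.1 says that Arm 1's decisions are made as section 4.2 describes. Section 14.1 also repeats the percentage rule for Arm 2. Every version except 13.3 uses a percentage and so already gives 34 of 42. On that view, 45 of 56 merely illustrates adequate compliance on the continuous schedule.

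Much of this stands. A reader might infer from 13.3 that the intermittent levels can never yield an RP2D, or that 4 mg BID will be selected on patients treated mainly at 2 mg. The documents do not support either inference, because nothing gives 13.3 precedence and the cross-reference in 14.1 favours 4.2.

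The window is also narrow. Reductions under Table 4 follow a hold, so the event must resolve within about five days. A cut without a hold rests on investigator discretion alone. Section 15.3 adds that "clinically important or persistent toxicities not included above may also be considered a DLT at the discretion of the investigator", which removes the discrepancy whenever it is used, and the investigators review all available safety data at each step.

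Two things remain. 13.3 is wrong as written for two dose levels. The cross-reference does not settle the dose-level question for 14.1's own DLT population or for Arm 2, whose wording can be read either way. Safety review and the discretionary clause do not define the denominator when no DLT is called.

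**Conclusion.** The point holds as a minor inconsistency. The arithmetic against 13.3 on the intermittent levels is certain and needs no assumption, although those levels open only after de-escalation. The conflict over dose level is real and reachable through the protocol's own dose-modification rules, and it leans only towards the higher dose. Its effect on the RP2D is small: at an assumed 20% DLT rate, 65.5% against 63.0% at q = 5% and 60.1% at q = 10%. Nothing in the documents anchors q, so a claim that dose selection is materially biased would go too far.

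**What to change.** Replace the fixed count in 13.3 with the Arm 1 rule from 4.2, and align 14.1 and the Arm 2 text of 4.2 with it. A patient is evaluable after taking, at the assigned dose level, at least 80% of the Cycle 1 doses planned for that schedule (45 of 56 continuous, 34 of 42 intermittent), plus both fulvestrant doses in Arm 1, or after a DLT. Whether an early reduction should itself count as a DLT is a separate design choice and need not be decided here.

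The change is wording only. Its cost is a fraction of a patient per level: 6/(1 − q) = 6.1, 6.3 and 6.7 treated per six evaluable at q = 2%, 5% and 10%.

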1. Mirdametinib starting dose Dose Level 1 (4 mg BID PO given continuously)
 - a. Up to 3 subjects will be treated with mirdametinib 4 mg BID PO given continuously in combination with the recommended dose of fulvestrant.
 - b. If ≤ 1 of the first 3 evaluable subjects in Dose Level 1 exhibit a DLT in Cycle 1, then Dose Level 1 will be expanded (see #2 below).
 - c. Mirdametinib dose in combination with fulvestrant will not be escalated above the 4 mg BID dose level.
2. Dose Level 1 expansion:
 - a. A sufficient number of subjects will be treated with mirdametinib 4 mg BID PO given continuously in combination with the recommended dose of fulvestrant to accrue 6 evaluable subjects.
 - b. If ≤ 1 of 6 evaluable subjects in the starting Dose Level exhibit a DLT in Cycle 1, then **mirdametinib 4 mg BID PO** given continuously will be declared as the recommended dose for Part 2 (RP2D) in combination with fulvestrant.
 - c. If ≥ 2 of the first 3 evaluable subjects or ≥ 2 of the 6 evaluable subjects in Dose Level 1 exhibit a DLT in Cycle 1, then the mirdametinib dose will be de-escalated (see #3 below, Dose Level -2).

Memorial Sloan Kettering Cancer Center
[name]
[name]

3. Mirdametinib Dose Level -2 (de-escalation Dose Level at 2 mg BID PO given continuously)
 - a. Up to 3 subjects will be treated with mirdametinib 2 mg BID PO given continuously in combination with the recommended dose of fulvestrant in Dose Level -2
 - b. If 1 of the first 3 evaluable subjects in Dose Level -2 exhibit a DLT in Cycle 1, then a sufficient number of subjects will be treated with mirdametinib 2 mg BID PO given continuously in combination with the recommended dose of fulvestrant to accrue 6 evaluable subjects.
 - c. If ≤ 1 of 6 evaluable subjects in Dose Level -2 exhibit a DLT in Cycle 1, then **mirdametinib 2 mg BID PO** given continuously will be declared as the recommended dose for Part 2 (RP2D) in combination with fulvestrant.
 - d. If ≥ 2 of the first 3 evaluable subjects or ≥ 2 of the 6 evaluable subjects in Dose Level -2 exhibit a DLT in Cycle 1, then the Arm 1 will be further de-escalated (see #4 below).
4. Mirdametinib Dose Level -2INT (de-escalation Dose Level at 2 mg BID PO on a 3 weeks on, 1 week off schedule)
 - a. Up to 3 subjects will be treated with mirdametinib 2 mg BID PO given intermittently in combination with the recommended dose of fulvestrant in Dose Level -2INT

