 - b. If 1 of the first 3 evaluable subjects in Dose Level -2INT exhibit a DLT in Cycle 1, then a sufficient number of subjects will be treated with mirdametinib 2 mg BID PO, intermittently dosed, in combination with the recommended dose of fulvestrant to accrue 6 evaluable subjects.
 - c. If ≤ 1 of 6 evaluable subjects in Dose Level -2INT exhibit a DLT in Cycle 1, then **mirdametinib 2 mg BID PO**, intermittently dosed, will be declared as the recommended dose for Part 2 (RP2D) in combination with fulvestrant.
 - d. If ≥ 2 of the first 3 evaluable subjects or ≥ 2 of the 6 evaluable subjects in Dose Level -2 exhibit a DLT in Cycle 1, then the Arm 1 will be discontinued. The reason for discontinuation of Arm 1 will be that 2 mg BID PO, dosed intermittently, is deemed to be the minimum dose required for sufficient clinical benefit from mirdametinib in combination with fulvestrant in the refractory metastatic breast cancer.

Arm 1 - Part 2 (Expansion Cohorts)

The following expansion treatment groups (up to 28 subjects each). Both cohorts are planned and the rationale for sample size is included in section 14.5. These will initially be started, either in parallel or sequentially depending on the results of Part 1:

Memorial Sloan Kettering Cancer Center
[name]
[name]

1. Subjects with hormone receptor-positive, HER2-negative metastatic breast cancer exhibiting NF1 loss defined as homozygous deletion of NF1 by NGS assay; truncating or nonsense mutations in NF1; OncoKB defined pathogenic missense mutation; OncoKB defined activating mutation in KRAS or HRAS.
2. Subjects with hormone receptor-positive, HER2-negative metastatic breast cancer exhibiting EGFR amplification defined as >1.9 copies of EGFR by NGS assay; ERBB2 hotspot somatic mutation defined as activating by OncoKB.

The above expansion treatment groups are prioritized for this study, however as an exploratory treatment group to be considered in the future is the following cohort:

1. Subjects with hormone receptor-positive, HER2-negative metastatic breast cancer exhibiting OncoKB defined activating mutations in BRAF, CRAF, or MEK1/2

Arm 2 – Part 1 (Dose escalation of mirdametinib as single agent)

Part 1 will be conducted in three sequential Dose Level escalations according to the 3+3 design based on the incidence of dose-limiting toxicities (DLT) and the overall safety profile of the study treatments. The DLT definitions are listed in [Section 15.3](#).

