Dose Level -1	3mg PO BID given continuously
Dose Level 1	4mg PO BID given continuously
Dose Level 2	6mg PO BID given continuously
Dose Level 3	8mg PO BID given continuously

In arm 1, dose level 1 of mirdametinib will be used in the safety run-in with fulvestrant and this dose will be used as the RP2D, otherwise dose de-escalation will be carried out. In this arm if that dose is not tolerated, this will proceed to dose level -2 with fulvestrant. If dose level -2 is not tolerated, dose level -2INT will be initiated. Arm 2 will follow a dose escalation 3+3 standard design, in which dose level 1 is the initial dose of mirdametinib, with additional dose levels 2 and 3. Pending DLTs in dose levels 1-3, this arm will proceed to dose level -1 using mirdametinib as monotherapy. If dose level -1 is not tolerated, dose level -1INT will be initiated.

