fulvestrant. If 1 of the first 3 evaluable subjects in Dose Level -2INT exhibit a DLT in Cycle 1, then a sufficient number of subjects will be treated with mirdametinib 2 mg BID PO on a 3 weeks on, 1 week off schedule, in combination with the recommended dose of fulvestrant to accrue 6 evaluable subjects. If 1 of 6 evaluable subjects in Dose Level -2INT exhibit a DLT in Cycle 1, then **mirdametinib 2 mg BID PO on a 3 weeks on, 1 week off schedule**, will be declared as the recommended dose for Part 2 (RP2D) in combination with fulvestrant. If ≥ 2 of the first 3 evaluable subjects or ≥ 2 of the 6 evaluable subjects in Dose Level -2INT exhibit a DLT in Cycle 1, then Arm 1 will be discontinued. In the case of de-escalation there will be at least 18 evaluable patients (6 from dose level 0, and 6 on two separate dose levels of de-escalation).

Arm 2

Part 1 will be conducted in three sequential Dose Level escalations according to the 3+3 design based on the incidence of dose-limiting toxicities (DLT) and the overall safety profile of the study treatments. At each step of the 3+3 design, the investigators will review all available safety and PK data in the current Dose Level and decide about the appropriate next step. The subjects will become evaluable for the 3+3 decisions if they complete Cycle 1 and receive at least 80% of assigned drug doses, or if they exhibit a DLT in Cycle 1. The starting dose of mirdametinib as single agent in each dose escalation dose level will be as follows: mirdametinib 4 mg BID PO given continuously, mirdametinib 6 mg BID PO given continuously, mirdametinib 8 mg BID PO given continuously. The de-escalation Dose Levels (Dose Level -1) may evaluate mirdametinib 3 mg BID given continuously and (Dose Level -1INT) may evaluate mirdametinib 3 mg BID given on. 3 weeks on, 1 week off schedule.

The 3+3 decisions in Part 1 of Arm 2 will be made similar to the above. Up to 3 subjects will be treated with mirdametinib as single agent at the dose of **4 mg BID PO** given continuously. If ≤ 1 of the first 3 evaluable subjects in Dose Level 1 exhibit a DLT in Cycle 1, then Dose Level 1 will be expanded. If 0 of the first 3 evaluable subjects in Dose Level 1 exhibit a DLT in Cycle 1, then the dose of mirdametinib as single agent will be escalated to Dose Levels 2 and 3 (**6 mg BID** given continuously **and 8 mg BID** given continuously) following the same rules as above. There will thus be as many as 18 evaluable patients on this arm.

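### The Arm 1 toxicity stopping rule in section 4.2 (step 4d) names Dose Level -2 where -2INT is meant, and so conflicts with step 3d and section 14.1

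*Combined protocol and SAP*

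**What the plan says.** Section 4.2 gives the Arm 1 Part 1 rules as numbered steps.

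- **Step 3** covers Dose Level -2 (2 mg BID, continuous). Under 3d, two or more DLTs among the first three or among six evaluable subjects "in Dose Level -2 exhibit a DLT in Cycle 1, then the Arm 1 will be further de-escalated", with a pointer to step 4.
- **Step 4** is headed "Mirdametinib Dose Level -2INT (de-escalation Dose Level at 2 mg BID PO on a 3 weeks on, 1 week off schedule", and 4a to 4c all name -2INT. Step 4d then says that the same DLT counts "in Dose Level -2 exhibit a DLT in Cycle 1, then the Arm 1 will be discontinued". Its next sentence gives the reason: "2 mg BID PO, dosed intermittently, is deemed to be the minimum dose required for sufficient clinical benefit".

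Two other sections cover the same sequence. Section 10.1 says: "If dose level -2 is not tolerated, dose level -2INT will be initiated". Section 14.1 repeats the 3+3 rules in prose. It sends a failed Level -2 on to further de-escalation and places the closing rule one level lower, where the stated DLT counts "in Dose Level -2INT exhibit a DLT in Cycle 1, then Arm 1 will be discontinued".

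**The concern.** Steps 3d and 4d have the same trigger at the same named level but different actions: 3d opens -2INT and 4d closes the arm. The conflict is complete, because step 4 can be entered only through 3d. Read literally, 4d is therefore already satisfied whenever step 4 opens, and the intermittent level could never be tested. Section 4.2 says that intermittent levels were added in case continuous dosing is poorly tolerated, and the literal reading would cancel that provision.

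The misprint also leaves a gap. Step 4c withholds an RP2D at -2INT unless at most one of six subjects has a DLT, but no clause in section 4.2, as labelled, says that the arm stops if -2INT fails.

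Section 4.2 is the operational rule set, and section 14.1 refers back to it. The clause that closes an arm for toxicity should not need to be reconciled with other sections before it can be applied.

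**Working it through.** **Text comparison**

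| Place | Level named | Action on ≥2 of 3 or ≥2 of 6 DLTs |
|---|---|---|
| 4.2, step 3d | -2 | De-escalate to step 4 |
| 4.2, step 4d | -2 (under a -2INT heading) | Discontinue Arm 1 |
| 10.1 | -2 (described as not tolerated) | Start -2INT |
| 14.1 | -2 | De-escalate further |
| 14.1 | -2INT | Discontinue Arm 1 |

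Step 4d is the only entry out of line. Lost characters in the PDF text are an unlikely cause, since the INT suffix is intact in 4a to 4c. The parallel Arm 2 step uses a generic term for the de-escalation level, so it names no wrong level.

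**How often the clause would be met (illustration)**

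The documents give no expected DLT rate for these levels, so p = 0.2 and p = 0.3 are assumptions.

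*Check against the plan's own table.* Under the usual 3+3 convention a level passes with probability (1−p)³ + 3p(1−p)²·(1−p)³. For p = 0.1 to 0.5 this gives 0.91, 0.71, 0.49, 0.31 and 0.17. These agree after rounding with the escalation table in section 14.1 (0.9, 0.7, 0.5, 0.3, 0.2).

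*Level -2 fails, 0 of 3 passing without expansion:*
- p = 0.2: 1 − [0.512 + 0.384 × 0.512] = 0.291
- p = 0.3: 1 − [0.343 + 0.441 × 0.343] = 0.506

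Step 3b covers only one outcome ("If 1 of the first 3 evaluable subjects in Dose Level -2 exhibit a DLT in Cycle 1, then a sufficient number of subjects"), so letting 0 of 3 pass is 3+3 convention and not the text of 3b.

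*Level -2 fails, six always treated.* The patient count in section 14.1 ("6 on two separate dose levels of de-escalation") could suggest this reading. Failure is 1 − P(X ≤ 1 | n = 6, p):
- p = 0.2: 1 − 0.655 = 0.345
- p = 0.3: 1 − 0.420 = 0.580

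*From the start of the arm.* Level 1 is expanded to six if at most one of the first three has a DLT, so it fails with the same 0.345 or 0.580. With equal DLT risk at Level 1 and Level -2:
- p = 0.2: 0.345 × 0.291 = 0.100 to 0.345 × 0.345 = 0.119
- p = 0.3: 0.580 × 0.506 = 0.293 to 0.580 × 0.580 = 0.336

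*Literal against intended rule, once Level -2 is open.* Under the literal 4d the arm closes with probability 0.291 or 0.506. Under the intended rule both -2 and -2INT must fail: 0.291² = 0.085 or 0.506² = 0.256, assuming equal risk at both levels and independent cohorts.

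**The case against.** The strongest reply is that section 4.2 corrects itself. Step 3d points to step 4, so a user arrives there only after Level -2 has failed. If 4d really meant Level -2, then 4a to 4c could never operate, and the reason sentence in 4d already speaks of intermittent dosing. Sections 10.1 and 14.1 give the right sequence, investigators review all safety and PK data at each step, and the DSMC oversees the trial. On this view the point is editorial, and the probabilities lend weight to a typing slip.

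Most of this stands. The intent can be recovered from step 4 alone, and no likely path to a wrong decision has been shown. The probabilities do not measure harm. The 29% and 51% figures rest on convention for the 0-of-3 outcome. The figures from the start of the arm assume that halving the dose leaves DLT risk unchanged, so for a given Level 1 risk they overstate the chance if toxicity falls.

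None of this makes the printed clause correct. It names the wrong level in the rule that closes an arm for toxicity, and it contradicts the step before it.

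**Conclusion.** The point holds. Step 4d carries the wrong dose-level label. The contradiction with step 3d and section 14.1 is certain from the text, and the intended level, -2INT, is not in doubt. The practical consequence is small: an avoidable query or misreading during a DLT decision, with no effect on sample size, power, error rates or endpoints. It should be corrected because it sits in an operational safety stopping rule. That conclusion rests on the wording alone and on none of the assumed DLT risks.

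**What to change.** In section 4.2, Arm 1 Part 1, step 4d, replace Dose Level -2 with Dose Level -2INT. The sequence then runs from Level 1 to -2, from -2 to -2INT, and from a failed -2INT to discontinuation, matching sections 10.1 and 14.1. The cost is one label, with no change to design, sample size or conduct. The contradiction needs no other edit. Whether steps 3b and 4b should also state what follows 0 of 3 DLTs is a separate question.
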